visit their private gynecologists for examinations and/or treatment rather than the study investigators represent missed opportunities to observe endpoints. If these subjects develop HPV 16- or 18-related CIN 2/3 or worse during the time that they missed study visits or if they had HPV 16- or 18-related CIN 2/3 or worse identified and treated outside of the study, then these events would not be captured in the primary estimate of the vaccine efficacy in this study.

To summarize compliance with respect to follow-up study visits, the numbers of subjects who complete each follow-up visit will be tabulated by treatment group. To provide measures of compliance with respect to follow-up study visits, the average interval between scheduled study visits will be computed for each subject and across subjects within a treatment group. The number of subjects with intervals longer than 9 months will be summarized by treatment group. In addition, the percentages of subjects in each group who had biopsies or excision procedures performed outside of the study will be summarized, and the percentages of subjects in each group who had biopsies or excision procedures performed outside of the study for whom the tissue samples were unavailable to Merck will be summarized. Differences in these measures between the treatment groups will be assessed observationally and the potential impact on the efficacy analyses will be noted. In addition, a sensitivity analyses for assessing the potential impact of missing data on the primary efficacy analysis is proposed in Section VII.D.1.f.

IV. IMMUNOGENICITY ANALYSES

A. Immunogenicity Endpoints

For immunogenicity, the endpoints of primary interest are:

1. the percentage of subjects who achieve anti-HPV 6 ≥ 200 mMU/mL, anti-HPV 11 ≥ 200 mMU/mL, anti-HPV 16 ≥ 200 mMU/mL, and anti-HPV 18 ≥ 200 mMU/mL at Week 4 Postdose 3 and
2. the GMTs to HPV 6, 11, 16 and 18 at Week 4 Postdose 3.

Of secondary interest are the GMTs to HPV 6, 11, 16 and 18 at Months 24 and 48. These variables will be measured only in the subjects participating in the consistency lot substudy.

Exploratory endpoints of interest are: (1) the immune responses to each vaccine HPV type in subjects who are baseline positive for that type and (2) the associations among vaccine HPV types.

B. Study Participant Populations for Immunogenicity Analyses

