In the case of equal follow-up in the vaccine and placebo groups, the point estimate for p is $C_v/(C_v + C_p)$. The lower bound of the $100(1-\alpha)\%$ exact confidence interval for p can be calculated by searching for the p_L such that the probability of observing C_v or more vaccine cases out of C_v+C_p total cases is $\alpha/2$. The upper bound of the exact confidence interval for p can be calculated by searching for p_U such that the probability of observing C_v or fewer vaccine cases out of C_v+C_p total cases is $\alpha/2$. It follows that the exact confidence interval for vaccine efficacy will then have lower bound $VE_L = (1-2*p_U)/(1-p_U)$ and upper bound $VE_U = (1-2*p_L)/(1-p_L)$.

In the event that there is unequal follow-up between groups, the estimate of the vaccine efficacy will rely not solely on the ratio of the number of cases in the vaccine group to the number of cases in the placebo group, but must also account for the follow-up in each group. Rather than $VE = 1 - C_v/C_p$, the point estimate for the vaccine efficacy will be $VE = 1 - (C_v/k_v)/(C_p/k_p)$, where k_v and k_p are the person years of follow-up in the vaccine and placebo groups, respectively. The following formulas will be used for the endpoints of the confidence interval for the vaccine efficacy: lower bound $VE_L = (1-p_U/k)/(1-p_U)$ and upper bound $VE_U = (1-p_L/k)/(1-p_L)$, where $k = k_v/(k_v + k_p)$, Follow-Up in Vaccine Group/Total Follow-Up.

D. Statistical Methods (Cont.)**b. Counting of Efficacy Endpoints**

Subjects will be counted only once for the primary efficacy analysis. If a subject develops CIN 2/3 related to HPV 16 at Year 2 and develops CIN 2/3 related to HPV 18 at Year 3, the subject will be counted as one CIN 2/3 endpoint in the primary efficacy analysis. For the efficacy summaries by HPV type, the subject will be counted once in the HPV 16-related CIN 2/3 analysis and once in the HPV 18-related CIN 2/3 analysis.

c. Computation of Follow-Up Time

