In the primary per-protocol analysis, follow-up for CIN 2/3 and cervical cancer begins following the Month 7 visit. Therefore, each subject's follow-up time will be computed by calculating the number of days between her Month 7 visit date and her final visit date. For cases, the "final visit" will be the first visit at which CIN 2/3 or cervical cancer was detected for the purpose of person-time computation. This value will be converted to person-years by dividing by 365.25. To obtain the total follow-up time in each treatment group, k_v and k_p , the person-years will be summed over all subjects in the given treatment group.

Although the primary analysis is per-protocol and HPV type-specific, all subjects who are eligible for the per-protocol analysis based on at least 1 of the 2 HPV types being analyzed (HPV 16 or 18) will contribute follow-up time to the totals. For the exploratory analysis of all CIN 2/3, all subjects who are eligible for the per-protocol analysis based on at least 1 high-risk HPV type will contribute follow-up time to the totals.

d. Correlates of Protection

In addition to the methods described in Section III.C.3.c. for assessing the anti-HPV serum RIA responses as potential correlates of protection, the odds of developing breakthrough HPV 16/18-related CIN 2/3 or worse may be modeled as a function of the corresponding Postdose 3 RIA titers using a logistic regression model. Length of postvaccination follow-up and study site will be included as additional model terms. Statistical significance of the coefficient for the RIA titer will be an indication that RIA titer is a predictor of breakthrough

D. Statistical Methods (Cont.)

infection. The estimate of the coefficient will indicate the nature of the relationship. If there are few cases among the vaccine recipients, there may be insufficient information to establish an immune correlate of protection in this study.

e. Potential Bias**1) Ascertainment Bias**

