With respect to counting cases of CIN 2/3 and cervical cancer for the efficacy analyses, if a subject has a biopsy, ECC, or LEEP/conization specimen collected during the efficacy evaluation phase (post-Month 7) and the PCR result or pathology panel diagnosis is missing for the specimen, then the subject cannot be classified as a case based on that specimen.

When the missing data are needed to establish a subject's eligibility for analysis, the following rules will apply:

- With respect to missing serology results, subjects who are missing a baseline RIA result for a particular vaccine HPV type *will not* be eligible to be classified as cases of CIN 2/3 or cervical cancer related to that HPV type in the primary analysis.
- With respect to missing PCR results for cervicovaginal specimens, a subject's eligibility for analysis depends on the number of missing results. In Protocol 015, the PCR results for 2 cervicovaginal specimens collected at enrollment and 2 cervicovaginal specimens collected at Month 7 are used to determine each subject's eligibility for analysis. Subjects who are missing one or both of the PCR results for a given vaccine HPV type at enrollment or Month 7 will not be eligible to be cases of CIN 2/3 or cervical cancer related to that HPV type in the primary analysis.
- If the PCR result from a biopsy sample taken between enrollment and Month 7 (inclusive) is missing for a given vaccine HPV type, and the biopsy is diagnosed as abnormal, the subject *will not* be eligible to be classified as a case of CIN 2/3 or cervical cancer related to that type. If the PCR result is missing and the diagnosis is normal, the subject *will* be eligible. This rule was established because abnormal tissue is likely to be HPV PCR positive.

Similar rules will be applied for the secondary analysis.

Missing data which results from a subject dropping out of the study will be treated as missing (non-existent) in the primary analysis. However, a sensitivity analysis will be conducted in which the number of cases expected among subjects who are lost to follow-up will be projected assuming that these subjects would have been classified as cases with the same probability as those subjects who were not lost to

D. Statistical Methods (Cont.)

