follow-up. In this analysis, it will be assumed that subjects who are lost to follow-up prior to Month 7 (i.e., prior to completion of the vaccination series) would have been classified as cases at the same rate as the placebo recipients in the primary analysis regardless of treatment group. That is, an assumption of “no vaccine efficacy” will be made in subjects who do not complete the vaccination regimen. The incidence rate that will be assumed for subjects who are lost to follow-up at Month 7 or following Month 7 (i.e., after completion of the vaccination series) will depend on each subject’s treatment group. It will be assumed that vaccine recipients who complete the vaccination series and then drop out subsequently would have developed the endpoint of interest at the same rate as the vaccine recipients in the primary analysis (who will all have also completed the vaccination series). It will be assumed that placebo recipients who complete the vaccination series and then drop out subsequently would have developed the endpoint at the same rate as the placebo recipients in the primary analysis.

g. Interaction

Prior to conducting the formal statistical analyses described above, tests for study site by treatment group interaction will be performed. This section describes the general approach that will be taken for assessing the presence and nature of the interactions.

All interaction tests will be conducted at the $\alpha = 0.10$ level. If no statistically significant interaction is found, then the study sites will be pooled for the analysis. If a significant treatment-by-study center interaction is found, the nature of the interaction will be examined and the relevance of the interaction in the context of the planned analysis will be evaluated. If the interaction cannot be disregarded, certain study sites may be analyzed separately.

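### In the missing-data sensitivity analysis (SAP VII.D.1.f), the part for subjects lost at or after Month 7 repeats the primary analysis's own assumption and so cannot move the efficacy estimate

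*SAP*

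**What the plan says.** SAP III.D, on compliance with follow-up visits, states that "sensitivity analyses for assessing the potential impact of missing data on the primary efficacy analysis is proposed in Section VII.D.1.f".

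SAP VII.D.1.f first fixes the primary rule: "Missing data which results from a subject dropping out of the study will be treated as missing (non-existent) in the primary analysis". It then adds that "a sensitivity analysis will be conducted in which the number of cases expected among subjects who are lost to follow-up will be projected", in two parts:

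- **Lost before Month 7.** Both arms get the placebo rate from the primary analysis, which means no vaccine efficacy for those who did not complete the series.
- **Lost at or after Month 7.** Vaccine recipients "would have developed the endpoint of interest at the same rate as the vaccine recipients in the primary analysis"; placebo recipients "would have developed the endpoint at the same rate as the placebo recipients in the primary analysis".

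The primary estimator is set elsewhere. Under VII.D.1.c a subject's "follow-up time will be computed by calculating the number of days between her Month 7 visit date and her final visit date". Under VII.D.1.a, VE is one minus the ratio of cases per person-year in the two arms.

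**The concern.** A rate per person-year drops the time after a subject leaves. The estimate then describes the whole arm only if the unseen time carries the same event rate as the observed time in that arm. A sensitivity analysis for dropout should ask what happens when that is not so. For subjects lost at or after Month 7 the plan makes the same assumption again.

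These are the dropouts inside the per-protocol set, because follow-up there starts at Month 7. If late dropout were related to risk, or differed between arms, this part of the check would still report no effect, and a reader could take the unchanged figure as evidence of robustness. No other analysis in the SAP varies the outcome of ordinary late dropouts. The modified intention-to-treat sets change who is eligible. The analyses of outside specimens, of the central-laboratory diagnosis and of the more severe diagnosis change which specimens or diagnoses count.

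**Working it through.** **Plan's own figures.** The SAP gives no numerical result for this sensitivity analysis. Its exact conditional method can be checked against Table 7. With success at 4 or fewer vaccine cases of 19, and 8 or fewer of 29, power at true VE 80/85/90% is 80.1/90.9/97.6% and 95.9/99.1/99.9%. Table 7 gives 80/90/97% and 95/99/>99%, so the method is read correctly.

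**The identity.** Let an arm have C cases in k observed person-years and m person-years lost after Month 7. Own-arm projection adds (C/k)m cases:

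(C + (C/k)m) / (k + m) = C(k + m) / [k(k + m)] = C/k

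Each arm's rate is unchanged, so VE is unchanged for any m in either arm. A numerical check at 0, 2, 5 and 8 vaccine cases of 29, with late loss (vaccine/placebo) of 16/16%, 25/10% and 10/25%, gave a change of 0.0 points every time.

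**Inputs for the size.**
- Attrition of at most 15% through Month 7 and at most 5% per year afterwards (VII.A.1, assumption c).
- Follow-up of 41 months (assumption e).
- A dropout is at risk for half the time (assumption d).
- 29 cases at the final analysis; two-sided alpha 0.0411.
- Assumed for illustration: true VE 85%, equal arms, and early dropouts eligible in the same proportion as the rest.

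**Late dropout alone.**
- Lost: 1 − 0.95^(41/12) = 16.1%. Person-time missing: 16.1%/2 = 8.04%.
- Missing relative to observed: 0.0804/0.9196 = 0.0874.
- Cases at VE 85%: vaccine 29 × 0.15/1.15 = 3.78; placebo 25.22.
- Own-arm rule: 3.78 × 1.0874 = 4.11 against 25.22 × 1.0874 = 27.42, so VE = 85.0%.
- Placebo rate for late vaccine dropouts: 3.78 + 0.0874 × 25.22 = 5.99 against 27.42, so VE = 1 − 5.99/27.42 = 78.2%.

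**Early and late together.** Early dropouts miss the whole follow-up, so at the placebo rate they add (0.15/0.85)/0.9196 × 25.22 = 4.84 cases per arm.
- Plan: (4.11 + 4.84)/(27.42 + 4.84) = 8.95/32.26, so VE is about 72.2%.
- Late vaccine dropouts also at the placebo rate: (5.99 + 4.84)/32.26 = 10.83/32.26, so VE is about 66.4%.

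**Lower bounds.** VII.D.1.f names no interval method. If projected cases were entered in the exact formula as though observed, the bounds at alpha 0.0411 would be:

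| Split (vaccine v placebo) | Primary | Own-arm projection | Late vaccine dropouts at placebo rate |
|---|---|---|---|
| 4 v 25 | 52.0% | 54.1% | about 43% |
| 8 v 21 | 7.7% | 11.1% | 2.6% |

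**The case against.** The strongest reply is that the analysis as a whole is not inert. Giving all early dropouts zero efficacy takes VE from 85% to about 72.2% in the worked case, a larger step than the further 6 points or so from a stricter late rule. The larger source of loss, up to 15% of subjects before Month 7, gets the stringent assumption. This stands, and it is why the point is confined to the late component. A reader might infer that the SAP has no real missing-data sensitivity analysis; the early rule shows otherwise.

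The late projection also does something in combination. It completes the cohort and so changes the weight of the early dropouts: at 5 v 24 cases, VE with the early rule alone is 66.4%, and 67.3% once the late own-arm cases are added. That is true, but the shift dilutes the early penalty and tests nothing about late dropout.

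The own-arm rate is moreover a reasoned choice: these women completed the series, as did all vaccine recipients in the primary analysis, and subjects and sites stay blinded. That makes it a sensible base case. It does not make it a stress test, since it is the base case already in use.

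VII.D.1.f first speaks of equal probability and only later of equal rate. If a per-subject probability were applied, VE would still not move under equal loss. Under 25/10% loss it would shift by up to about 4 points, but only because time already observed is ignored.

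Finally, a reader might infer that the plan narrows its interval by counting projected cases. The SAP does not say so, and the bounds shown for projected cases are conditional on that reading.

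**Conclusion.** The point holds for the late-dropout component only. That component leaves VE unchanged by algebra, on the equal-rate wording, and needs no assumption about the amount or balance of loss. The sizes do rest on assumptions: VE 85%, 29 cases, attrition at the SAP's ceilings and half the follow-up missing per late dropout. On these, the untested contrast is 85.0% against 78.2% for late dropout alone, and about 72.2% against 66.4% with early dropouts included. Lower attrition would shrink it.

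It would be tempting to conclude that the efficacy claim is at risk. The documents do not support that. Success requires a lower bound above 0%, and in the example near VE 85% (4 v 25) the bound stays at about 43% even with the placebo rate for late vaccine dropouts. At the borderline 8 v 21 split with equal loss it stays at 2.6%. This is a cheap improvement to a supporting analysis and leaves the primary test as it is.

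**What to change.** In VII.D.1.f, keep the present rules and add a scenario in which vaccine recipients lost at or after Month 7 get the placebo rate for their unobserved time, as the plan already does for early dropouts. Optionally add a tipping point: the multiple of the vaccine-arm rate among late vaccine dropouts at which the lower bound reaches 0%. Use one term, rate per person-year, throughout. If an interval is reported, say how it is formed and do not count projected cases as observed; multiple imputation of the projected cases would serve.

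The cost is a little programming and a less favourable sensitivity estimate. The primary analysis, alpha, sample size and decision rule are untouched.

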To assess the impact of treatment group-by-study center interaction on the incidence rates of the various disease endpoints, an exact test for homogeneity in relative risks among the study sites will be conducted using the method of Martin and Austin [2]. Due to the small numbers of cases of certain disease endpoints expected in this study, there will be low power to detect treatment group-by-study center interaction. Therefore, treatment group-by-study center interaction may need to be assessed observationally. If this is the case, any observed interaction will be described, but it may not be possible to analyze study sites separately and still maintain adequate power for the primary and secondary analyses.

D. Statistical Methods (Cont.)**2. Methods for Immunogenicity Analyses****a. Consistency of Immune Responses as Measured by Proportions**

The methodology of Wiens, Heyse, and Matthews [3] will be used to demonstrate consistency among the 3 separate lots of quadrivalent HPV (Types 6, 11, 16, 18) L1 VLP vaccine. According to this methodology, the evaluation of similarity in response rates (the proportions of subjects with anti-HPV ≥ 200 mMU/mL at 4 weeks Postdose 3) between lots will be based on 3 pairwise comparisons for each vaccine HPV type. For each HPV type, each pairwise comparison is intended to demonstrate the equivalence of 2 of the 3 lots within 10 percentage points using 2 one-sided tests at the $\alpha = 0.05$ level for an overall type I error rate of 0.05 as outlined in Table 8. The tests will be stratified by study center as described in Section VII.D.2.b. Since there are 3 consistency lots, there will be 6 one-sided comparisons for each vaccine HPV type.

Table 8

Comparisons for Establishing Consistency

Pairwise Comparison	Group 1	Group 2
1	Lot 1	Lot 2
2	Lot 1	Lot 3
3	Lot 2	Lot 3

Two lots will be considered similar if both one-sided p-values associated with the 2 comparisons within the pair are < 0.05 (corresponding to the rejection of the associated null hypothesis). This criterion is equivalent to requiring the two-sided 90% confidence interval for the difference in response rates between the pair of lots be entirely within (-10%, 10%). All 3 lots will be considered consistent with respect to response rates for a given vaccine HPV type if all 6 one-sided p-values for that vaccine HPV type are < 0.05 , or, equivalently, if all 3 pairwise 90% two-sided confidence intervals for the vaccine HPV type are entirely within (-10%, 10%).

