D. Statistical Methods (Cont.)**b. Equivalence With Respect to Proportions**

As described above in Section VII.D.2.a., the first primary immunogenicity hypothesis will be addressed by 3 pairs of one-sided tests for 2 binomial proportions conducted at the $\alpha = 0.05$ level for each vaccine HPV type. The tests will be stratified by study center.

The statistical hypotheses that will be tested are:

$$H_0: p_1 - p_2 \leq -S_0 \text{ or } p_1 - p_2 \geq S_0$$

$$H_a: -S_0 < p_1 - p_2 < S_0$$

where H_0 and H_a are the null and alternative hypotheses, respectively, p_1 and p_2 are the proportions of subjects with anti-HPV ≥ 200 mMU/mL at 4 weeks Postdose 3 for the HPV type of interest in the 2 quadrivalent HPV (Types 6, 11, 16, 18) L1 VLP vaccine lots being compared, and S_0 is the prespecified equivalence margin for the 2 proportions.

Statistical significance for the 2 one-sided equivalence tests for each pair of lots is established if the p-values for the hypothesis tests are each < 0.05 . This corresponds to the 90% confidence interval for $p_1 - p_2$ being entirely contained within the interval $(-S_0, S_0)$ where S_0 is 10 percentage points for this study. Since both one-sided tests for each pair of lots are required to reject the null hypothesis at the $\alpha = 0.05$ level, the overall α -level will be controlled at $\alpha = 0.05$ for each pair of lots.

The proposed method for testing equivalence is based on a test for a non-zero difference in binomial proportions by Miettinen and Nurminen [1] with stratification by study center. The test statistic (Z-statistic) is given by:

$$Z_{diff} = \frac{\hat{p}_1^* - \hat{p}_2^* - S_0}{\sqrt{\sum_{i=1}^I (W_i / \sum_{k=1}^K W_k)^2 \tilde{V}_i}} \quad \text{for the first one-sided test, and}$$

$$Z_{diff} = \frac{\hat{p}_1^* - \hat{p}_2^* + S_0}{\sqrt{\sum_{i=1}^I (W_i / \sum_{k=1}^K W_k)^2 \tilde{V}_i}} \quad \text{for the second one-sided test, (1)}$$

where

D. Statistical Methods (Cont.)

$$\hat{p}_s^* = \sum_{i=1}^I (W_i / \sum_{k=1}^K W_k) \hat{p}_{si} \quad \text{for } s=1, 2;$$

$$\tilde{v}_i = \left[\frac{\tilde{p}_{1i}(1 - \tilde{p}_{1i})}{n_{1i}} + \frac{\tilde{p}_{2i}(1 - \tilde{p}_{2i})}{n_{2i}} \right] \frac{(n_{1i} + n_{2i})}{(n_{1i} + n_{2i} - 1)} \quad (2);$$

and

\hat{p}_{1i} = observed proportion with the response of interest in Group 1 at study center i ;

\hat{p}_{2i} = observed proportion with the response of interest in Group 2 at study center i ;

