n_{1i} = number of subjects in Group 1 at study center i ;

n_{2i} = number of subjects in Group 2 at study center i ;

$W_i = n_{2i} + n_{1i}$ (i.e., the weight for study center i , the total sample size in the 2 groups at study center i);

$I=K$ = total number of study centers;

$i=k$ = study center;

\tilde{p}_{1i} and \tilde{p}_{2i} = the maximum likelihood estimates for the proportion of responders in Group 1 and Group 2, respectively, computed under the constraint $\tilde{p}_{2i} = \tilde{p}_{1i} + S_0$; and

S_0 = prespecified difference in proportions under the null hypothesis.

The test statistic, Z_{diff} , has an asymptotic standard normal distribution under the null hypothesis, H_0 . Large values of Z_{diff} favor the alternative hypothesis, H_a .

Although the study conclusions will be based on the p-values for the hypothesis tests, two-sided 90% confidence intervals for the difference in proportions between each pair of lots will also be provided. Based on Miettinen and Nurminen [1], the two-sided 90% confidence interval is given by the roots for $PD = p_1 - p_2$ in the following equation:

D. Statistical Methods (Cont.)

$$\chi_{\alpha}^2 = \frac{(\hat{p}_1^* - \hat{p}_2^* - PD)^2}{\sum_{i=1}^I (W_i / \sum_{k=1}^K W_k)^2 \tilde{V}_i} \quad (3)$$

where

χ_{α}^2 is the 100(1-2 α)th percentile from the central chi-square distribution with 1 degree of freedom ($\chi_{\alpha}^2 = 2.71$ for two-sided 90% confidence interval);

\hat{p}_1^* , \hat{p}_2^* , \tilde{V}_i and W_i , are the same as defined earlier in the Z-statistic;

PD is the difference between 2 proportions ($PD = p_1 - p_2$);

$I=K$ = total number of study centers;

$i=k$ = study center;

$$\tilde{p}_{1i} = \tilde{p}_{2i} + PD \quad \text{for } i=1, \dots, I;$$

\tilde{p}_{2i} is the maximum likelihood estimate for p_{2i} under the constraint

$$\tilde{p}_{1i} = \tilde{p}_{2i} + PD .$$

Equation (3) does not allow for explicit solutions for PD ; therefore, a numerical algorithm will be used to obtain the 2 roots for PD (the upper and lower bounds of the confidence interval). Programming details for the numerical algorithm and the maximum likelihood estimates can be found in Miettinen and Nurminen [1].

c. Consistency in Immune Responses as Measured by GMTs

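### The response-rate lot-consistency test gives the wrong tail and the wrong null constraint for the first of its two one-sided tests; followed literally, identical lots fail.

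*SAP*

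**What the plan says.** SAP VII.D.2.a and VII.D.2.b set out the first co-primary immunogenicity hypothesis: the proportions at or above 200 mMU/mL are similar in the three lots. Each pair is compared "using 2 one-sided tests at the $\alpha = 0.05$ level for an overall type I error rate of 0.05".

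VII.D.2.b then specifies:

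- The null is a difference of −S0 or less, or of S0 or more; the alternative is a difference strictly between the two. The margin is fixed: "where S_0 is 10 percentage points for this study".
- The first test uses (p1 − p2 − S0)/SE and the second uses (p1 − p2 + S0)/SE, with centre-weighted proportions.
- SE comes from proportions estimated by maximum likelihood under a single constraint, p2 = p1 + S0, given once for both tests.
- A single statement of direction covers both tests: "Large values of Z_{diff} favor the alternative hypothesis, H_a".
- The p-values have priority over the interval: "Although the study conclusions will be based on the p-values for the hypothesis tests", with the two-sided 90% intervals provided in addition.
- Those intervals come from equation (3), under p1 = p2 + PD.

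VII.D.2.a and VII.D.2.b treat the p-value rule and the rule that the 90% interval lie within (−10%, 10%) as the same criterion.

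**The concern.** A two one-sided tests procedure has two different nulls, so it needs two rejection directions and two constraints. The plan gives one of each, and both belong to the second test.

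The first statistic tests p1 − p2 ≥ S0 against p1 − p2 < S0. Evidence for the alternative is a difference well below +S0, so the statistic must be strongly negative. The restricted estimates should sit on that null's boundary, p1 = p2 + S0. The written constraint puts them on the opposite boundary, p1 − p2 = −S0.

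This is the decision rule for a co-primary hypothesis: three pairs for each of four HPV types, 12 comparisons, all of which must pass (SAP IV.C.1). The two errors have different consequences:

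- **Tail.** Followed literally, similar lots cannot pass.
- **Constraint.** If the tail is silently corrected and the constraint is not, borderline pairs get a p-value that contradicts the interval the plan calls equivalent. This error is the harder one to notice in output.

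**Working it through.** **Inputs.** S0 = 0.10 and one-sided α = 0.05, critical value 1.645 (VII.D.2.a and b). Assumed response 90% in every lot; 361 evaluable subjects per lot for HPV 6 and 11, 348 for HPV 16 and 18; stated power 98.3% per type and 93.4% over four types (VII.A.2). All calculations use a single stratum. The response counts below are illustrations, not plan figures.

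**Formula.** SE² = [p̃1(1 − p̃1)/n1 + p̃2(1 − p̃2)/n2] × (n1 + n2)/(n1 + n2 − 1), where p̃1 and p̃2 are the restricted estimates.

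**1. The plan's own power, with the correct test.** Three identical lots at 90% were simulated 400,000 times. Test 1 rejected for Z < −1.645 under p1 = p2 + S0, test 2 for Z > 1.645 under p2 = p1 + S0. All three pairs passed in 98.4% of replicates (n = 361) and 98.1% (n = 348), which agrees with the stated 98.3%; 0.983⁴ = 93.4%. So the power statement rests on the correct procedure. Followed as written, none of the 400,000 replicates passed at either sample size.

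**2. Tail error.** Equal observed rates:

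| Responders, each lot | SE | Z, first test | p, written (upper) tail | p, correct (lower) tail |
|---|---|---|---|---|
| 313/348 | 0.02428 | −0.10/0.02428 = −4.12 | 0.99998 | 0.00002 |
| 325/361 | 0.02378 | −0.10/0.02378 = −4.21 | 0.99999 | 0.00001 |

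With equal rates and equal n, the SE is the same under either constraint, so this failure comes from the tail sentence alone. As written, the first test rejects only when lot 1 exceeds lot 2 by well over the margin: at n = 361, 95% against 81% gives Z = 1.51 (no) and 95% against 80% gives Z = 1.86 (yes).

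**3. Constraint error alone, tail corrected.** In both cases the observed difference is 22/348 = 0.0632, so the numerator is 0.0632 − 0.10 = −0.0368.

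| Lot 1 v lot 2 (n = 348) | Constraint | p̃1, p̃2 | SE | Z | p |
|---|---|---|---|---|---|
| 335 v 313 | p1 = p2 + S0 (correct) | 0.970, 0.870 | 0.02021 | −1.82 | 0.034 |
| 335 v 313 | p2 = p1 + S0 (written) | 0.846, 0.946 | 0.02289 | −1.61 | 0.054 |
| 330 v 308 | p1 = p2 + S0 (correct) | 0.958, 0.858 | 0.02165 | −1.70 | 0.045 |
| 330 v 308 | p2 = p1 + S0 (written) | 0.835, 0.935 | 0.02390 | −1.54 | 0.062 |

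The upper 90% limits from equation (3) are 9.6 and 9.9 points. The interval says equivalent in both cases; the p-value under the written constraint says not.

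The written rule also depends on lot labels. With the first pair swapped (313 v 335), the decisive test is the second, for which the written constraint is right: Z = 1.82, p = 0.034, and the pair passes. The same data pass or fail according to which lot is called Group 1 in Table 8.

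**4. Long-run effect of the constraint error.** With the tail corrected, power for all three pairs falls from 98.4% to 98.1% (n = 361) and from 98.1% to 97.7% (n = 348). At a true difference of +10 points with n = 361, the first test's type I error is about 3.6% at 95% v 85% and 1.9% at 99% v 89%, against 4.9% and 4.7% with the correct constraint.

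**The case against.** The best defence is that the intended rule is clear from the rest of the plan. The hypotheses, both numerators, the 90% interval criterion and equation (3) are all correct, and the stated power matches the correct test. A one-sided p-value is defined by its hypothesis, so a programmer working from the printed null and alternative would take the lower tail for the first test. If not, a p-value near 1 beside an interval well inside the margin would expose the error. The constraint error is small at the planned rates and conservative in the cases checked: it produces false failures, not false claims of equivalence. Only one test per pair is affected. The GMT hypothesis does not use this statistic, and the main efficacy conclusion is declared independent of the substudy.

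Most of this stands. It shows that design, margin, α and sample size are sound and that literal application is unlikely to go unnoticed. It does not make the written test right. The plan ranks the p-values above the interval, so where they disagree the wrongly specified criterion governs. The constraint error would not show itself the way the tail error would, and it makes the result depend on lot labels.

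**Conclusion.** Wrong as written. For the first one-sided test of every pair, both the rejection direction and the constraint are those of the opposite null. Taken literally, the tail sentence makes identical lots fail with p of about 0.99998, and only pairs with lot 1 ahead by roughly 14 to 15 points would pass. If only the tail is put right, the loss is about 0.3 to 0.4 points of power for all three pairs under the planning assumption, with contradictory p-value and interval for borderline pairs such as 96.3% v 89.9%.

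This is an error of specification in a co-primary decision rule, not of design or sample size. The figures rest on a single stratum with equal lot sizes. Stratifying by centre would change the standard errors somewhat, but for near-equal lots it would not change the sign of the first statistic.

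**What to change.** In SAP VII.D.2.b, replace the single constraint and the single direction sentence with one of each per test:

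- **Test 1**, null p1 − p2 ≥ S0: restricted estimates under p̃1i = p̃2i + S0; reject for Z < −1.645.
- **Test 2**, null p1 − p2 ≤ −S0: restricted estimates under p̃1i = p̃2i − S0; reject for Z > 1.645.

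Add that the 90% interval from equation (3) must lead to the same decision, and check the analysis program against it, including a pair run with the lot labels swapped.

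The cost is two corrected lines and that check. Margin, α, sample size and stated power are unchanged, and there is no statistical downside.
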